2.2 Secondary objective(s)

Objective	Endpoint

To assess the efficacy of secukinumab 300 mg s.c. vs. placebo in patients with overuse rotator cuff tendinopathy in relieving symptoms over time	
WORC score at Weeks 2, 4, 8, 12, 18 and 24Disability of Arm, Shoulder and Hand Questionnaire (QuickDASH) score at Weeks 2, 4, 8, 12, 14, 18 and 24American Shoulder and Elbow Surgeons Shoulder Evaluation Form (ASES) score at Weeks 2, 4, 8, 12, 14, 18 and 24EQ5D-5L score at Weeks 2, 4, 8, 12, 14, 18 and 24Pain score using a VAS scale (considering the last 24 hours) at Weeks 2, 4, 8, 12, 14, 18 and 24Patient global assessment (PGA) score using a VAS scale (considering the last 24 hours), at Weeks 2, 4, 8, 12, 14, 18 and 24Physician global assessment (PhGA) score using a VAS scale (considering the last 24 hours), at Weeks 2, 4, 8, 12, 14, 18 and 24

To assess the structural changes in the rotator cuff tendinopathy over time	
MRI Sein score at Weeks 8, 14 and 24

To assess PK/immunogenicity in secukinumab treated patients	
PK/immunogenicity assessment at Day 1, Weeks 4, 12, 24

To confirm the safety and tolerability of AIN457 in patients with overuse rotator cuff tendinopathy over time	
Safety and tolerability assessments over time: Incidence and severity of AEs and SAEs; routine safety laboratory parameters

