4.1 Inclusion criteria

Patients eligible for inclusion in this study must fulfill all of the following criteria:

1. Written informed consent obtained prior to all study specific screening procedures, as close to the start of the screening period as possible
2. Male or non-pregnant, non-lactating female patients 18 to 65 years of age at randomization
3. Presence of unilateral rotator cuff tendinopathy with:
 - a. Symptoms present \geq 6 weeks, but $<$ 12 months prior to randomization
 - b. Tendinopathy with no more than a 50% tear as established by ultrasound at screening (historic data acceptable if not older than 3 months) and MRI at baseline: Sein MRI tendinopathy scoring system grade I-III; with no tear or partial tear [maximum 50% tendon thickness (Bauer tendon thickness score maximum 2); AP length maximum 10 mm (Bauer tendon length score max 2)]. Maximum 50% of patients with partial tear

- c. Pain in the affected shoulder (at rest or on movement) on at least 3 days out of 7 days in the past week prior to baseline and a score of ≥ 4 out of 10 on a VAS pain scale
- d. Positive “Painful Arc Test” on examination and/or nightly pain in the affected shoulder on at least 4 out of 7 days in the past week prior to baseline

4. The rotator-cuff tendinopathy must have been refractory to standard treatment defined as:
 - a. NSAIDs / acetaminophen
 - i. In the run-in period patients should be on a stable dose of NSAIDs and/or acetaminophen for at least 2 weeks prior to randomization, not exceeding – e.g.: Ibuprofen 1600 mg/d, naproxen 1000 mg, diclofenac 105 mg/d, or diclofenac sodium enteric-coated tablets 150 mg/d, or equivalent.
 - ii. If patients cannot tolerate these doses, the maximal tolerable dose should be used, and may be augmented with acetaminophen/paracetamol, at doses not exceed local guidelines or 4 g/day, whichever is lower. This medication should also be at a stable dose for at least 2 weeks.
 - iii. If patients have contraindications to NSAIDs or to acetaminophen, these treatments can be omitted (contraindication, drug and dose must be specified in the eCRF).
 - iv. If patients were refractory to at least 2 weeks of previous treatment as specified in 4 i/ii, NSAIDs or acetaminophen treatment can be omitted.
 - b. Physiotherapy

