8.4 Information to be collected on screening failures

Subjects who discontinue from the study prior to randomization are considered screen failures.

The reason for not being randomized and demographics will be entered in the CRF. The CRF for adverse events (AEs) should be completed for any Serious Adverse Events (SAEs) that occurred during the screening period. Adverse events that are not SAEs will be followed by the investigator and collected only in the source data.

All subjects who have signed informed consent and are randomized into the Treatment Period of the study will have all AEs **occurring after informed consent is signed** recorded on the CRF capturing AEs, and SAEs if applicable, i.e. when SAE criteria are met.

Investigators will have the discretion to record abnormal test findings on the medical history CRF whenever in their judgement, the test abnormality occurred prior to the informed consent signature.

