9.1 Adverse events

An adverse event (AE) is any untoward medical occurrence (i.e., any unfavorable and unintended sign [including abnormal laboratory findings], symptom or disease) in a subject after *providing written informed consent* for participation in the study until the end of study visit. Therefore, an AE may or may not be temporally or causally associated with the use of a medicinal (investigational) product.

In addition, all reports of intentional misuse and abuse of the study treatment are also considered an adverse event irrespective if a clinical event has occurred. See [Section 9.5](#) for an overview of the reporting requirements.

The occurrence of adverse events must be sought by non-directive questioning of the subject at each visit during the study. Adverse events also may be detected when they are volunteered by the subject during or between visits or through physical examination finding, laboratory test finding, or other assessments.

Abnormal laboratory values or test results constitute adverse events only if they fulfill at least one of the following criteria:

- They induce clinical signs or symptoms,
- They are considered clinically significant,
- They require therapy.

Clinically significant abnormal laboratory values or test results should be identified through a review of values outside of normal ranges/clinically notable ranges, significant changes from baseline or the previous visit, or values which are considered to be non-typical in patients with underlying disease. Investigators have the responsibility for managing the safety of individual subject and identifying adverse events. Clinically notable vital signs are defined in [Appendix 1](#).

Adverse events should be recorded on the Adverse Events CRF under the signs, symptoms or diagnosis associated with them, and accompanied by the following information:

1. The severity grade:
 - Mild: Usually transient in nature and generally not interfering with normal activities
 - Moderate: Sufficiently discomforting to interfere with normal activities
 - Severe: Prevents normal activities
2. Its relationship to the study treatment
 - Yes or
 - No
3. Its duration (start and end dates) or if the event is ongoing an outcome of not recovered/not resolved must be reported.
4. Whether it constitutes a SAE (see [Section 9.2](#) for definition of SAE) and which seriousness criteria have been met
5. Action taken regarding investigational treatment.

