7.2 Descriptive analyses

Patient demographics and other baseline characteristics

All data for background and demographic variables will be listed by treatment group and patient. Summary statistics will be provided by treatment group.

Relevant medical history, current medical conditions, results of laboratory screens, drug tests and any other relevant information will be listed by treatment group and patient.

Treatment

Data for study drug administration and concomitant therapies (including rescue medication) will be listed by treatment group and patient.

Vital signs

All vital signs data will be listed by treatment, patient, and visit/time and if ranges are available abnormalities (and relevant orthostatic changes) will be flagged. Summary statistics will be provided by treatment and visit/time.

ECG evaluations

All ECG data will be listed by treatment, patient and visit/time, abnormalities will be flagged. Summary statistics will be provided by treatment and visit/time.

Clinical laboratory evaluations

All laboratory data will be listed by treatment, patient, and visit/time and if normal ranges are available abnormalities will be flagged. A separate listing is provided presenting all parameters in a patient with any abnormal values. Summary statistics will be provided by treatment and visit/time.

Serum chemistries will include sodium, potassium, BUN/urea, bicarbonate, calcium, phosphorous, total protein, calcium, albumin, uric acid, creatinine, CK, total bilirubin, AST (SGOT), ALT (SGPT), GGT and alkaline phosphatase, at all timepoints specified in the Assessment schedule.

If the total bilirubin concentration is increased above 1.5 times the upper limit of normal, direct and indirect reacting bilirubin should be differentiated.

Triiodothyronine (T3), thyroxine (T4), thyroid-stimulating hormone (TSH), Rheumatoid factor (RF), anti-cyclic citrullinated peptide (anti-CCP) antibodies, and interferon-gamma release test done only at screening. FSH is only done at screening and only in patients who are reported post-menopausal at screening.

Adverse events

All information obtained on adverse events will be displayed by treatment group and patient. The number and percentage of patient s with adverse events will be tabulated by body system and preferred term with a breakdown by treatment. A patient with multiple adverse events within a body system is only counted once towards the total of this body system.

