Adverse event reporting for Clinical Trial Safety Disclosure (CTSD)

For the legal requirements of ClinicalTrials.gov and EudraCT, two required tables, 1) on treatment emergent adverse events which are not serious adverse events with an incidence greater than 0% and 2) on treatment emergent serious adverse events and SAE suspected to be related to study treatment, will be provided by system organ class and preferred term on the safety set population. These tables will be produced by Novartis.

The summary will be done by treatment i.e. active (AIN457) or Placebo.

If for a same patient, several consecutive AEs (irrespective of study treatment causality, seriousness and severity) occurred with the same SOC and PT:

- a single occurrence will be counted if there is ≤ 1 day gap between the end date of the preceding AE and the start date of the consecutive AE
- more than one occurrence will be counted if there is > 1 day gap between the end date of the preceding AE and the start date of the consecutive AE.

For occurrence, the presence of at least one SAE / SAE suspected to be related to study treatment / non SAE has to be checked in a block e.g., among AE's in a ≤ 1 day gap block, if at least one SAE is occurring, then one occurrence is calculated for that SAE.

The number of deaths resulting from SAEs suspected to be related to study treatment and SAEs irrespective of study treatment relationship will be provided by SOC and PT.

Pregnancy test

All pregnancy test results for pre-menopausal women who are not surgically sterile will be listed by treatment, patient and visit/time.

Tolerability of investigational treatments

Tolerability will be assessed by adverse events, laboratory values, injection site reaction and immunogenicity. The local tolerability at the site of s.c. injection of the study treatment will

be assessed in case of any local reaction, until this has disappeared. The assessment of pain, redness, swelling, induration, haemorrhage and itching will be recorded, capturing AEs, including the severity (mild, moderate, severe) and the duration of the adverse reaction. Data will be listed and summarized by treatment group.

Immunogenicity

All immunogenicity results for AIN patients will be listed by treatment, patient and visit/time.

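### The main adverse event table is not restricted to treatment-emergent events, although events are recorded from consent, and no general table by severity serves the safety endpoint

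*SAP*

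**What the plan says.** **Collection.** Under protocol 8.4, the CRF of a randomized patient takes every adverse event "occurring after informed consent is signed". Protocol 9.1 defines an adverse event from consent onward, "for participation in the study until the end of study visit". Protocol 4.1 requires "Written informed consent obtained prior to all study specific screening procedures, as close to the start of the screening period as possible". Table 8-1 puts screening at Days -49 to -22, run-in at Days -21 to -8, baseline at Days -7 to -1, first dose at Day 1 and the end of study visit at Day 169 ±7. Protocol 9.1 also has each event graded mild, moderate or severe, with start and end dates.

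**Endpoint.** Protocol 2.2 defines the secondary safety endpoint as "Incidence and severity of AEs and SAEs; routine safety laboratory parameters".

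**Main presentation.** The adverse event paragraph of SAP 7.2 has a listing rule ("All information obtained on adverse events will be displayed by treatment group and patient"), then the table rule: number and percentage of patients with events by body system and preferred term, broken down by treatment. Protocol 11.4.4 and 11.5.2 give the same table rule.

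**Other presentations in SAP 7.2.** The registry disclosure subsection plans two tables by system organ class, preferred term and arm on the safety set. One covers "treatment emergent adverse events which are not serious adverse events with an incidence greater than 0" percent; the other covers treatment-emergent serious events and related serious events. Deaths from serious events are also counted. Local tolerability data, recorded with severity and duration, are listed and summarized by arm.

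**The concern.** The CRF holds events from before any study drug was given, and the rule for the main table does not remove them. In that period patients may start physiotherapy and stabilise NSAID or acetaminophen intake, so events unrelated to study drug are plausible. Counted under each arm, they raise both incidences and draw the ratio towards 1.

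The main table and the registry tables would then follow different onset rules for the same patients, with no stated reconciliation.

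Severity is a separate gap. It is named in the endpoint and graded for every event, yet the general incidence table does not use it. A patient listing shows severity but does not summarise it by arm. The protocol intends the data to support Phase III planning, so the safety summary should match the endpoint.

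**Working it through.** The documents give no adverse event rates and no safety power, so there is no stated figure to reproduce. The check is a reading of the text, the window arithmetic and an illustration.

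**1. Does any rule remove pre-dose events from the main table?**
- Table rule (SAP 7.2; protocol 11.4.4 and 11.5.2): no onset condition.
- Safety set (SAP section 4; protocol 11.1): everyone who received study drug. This selects patients, not events.
- Treatment-emergent limit (SAP 7.2): used only for the registry tables, and not defined in the text provided.

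So nothing in the text removes them.

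**2. Length of the pre-dose window (Table 8-1)**
- Earliest scheduled start: 49/7 = 7.0 weeks before dosing.
- Latest scheduled start: 22/7 = 3.1 weeks before dosing.
- Share of the collection period, with 24 weeks = 168 days after first dose: 22/(22+168) = 11.6%; 49/(49+168) = 22.6%.

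Consent may slightly precede screening, and a footnote to Table 8-1 lets local rules prolong physiotherapy, so 7 weeks is the scheduled maximum, not a strict limit.

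**3. Size of the dilution (illustration)**

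Assumptions: incidence after first dose 60% active and 45% placebo over 24 weeks; constant rates; pre-dose rate in both arms equal to the placebo rate.
- Rate = -ln(1 - 0.45)/24 = 0.0249 per week.
- Tabulated incidence = 1 - (1 - p) × exp(-rate × pre-dose weeks), where p is the incidence after first dose.
- 22 days: exp(-0.0249 × 22/7) = 0.925. Active 1 - 0.40 × 0.925 = 63.0%; placebo 1 - 0.55 × 0.925 = 49.1%.
- 49 days: exp(-0.0249 × 7) = 0.840. Active 1 - 0.40 × 0.840 = 66.4%; placebo 1 - 0.55 × 0.840 = 53.8%.

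| Table | Active | Placebo | Difference (points) | Risk ratio |
|---|---|---|---|---|
| Onset after first dose | 60.0% | 45.0% | 15.0 | 1.33 |
| From consent, 22 days | 63.0% | 49.1% | 13.9 | 1.28 |
| From consent, 49 days | 66.4% | 53.8% | 12.6 | 1.23 |

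**4. Other assumed values, same formula with the rate reset to each placebo value**
- 65% vs 50%: ratio 1.30 falls to 1.25 (22 days) or 1.21 (49 days).
- One body system, 35% vs 20%: 1.75 falls to 1.65 or 1.56.
- One preferred term, 12% vs 4%: 3.00 falls to 2.76 or 2.54.
- 60% vs 45% with the pre-dose rate at half the placebo rate: the factors become exp(-0.0391) = 0.962 and exp(-0.0872) = 0.917, and the ratio falls to 0.615/0.471 = 1.31 or 0.633/0.496 = 1.28.

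**5. Severity.** The endpoint asks for incidence and severity of AEs and SAEs. Of the planned tables, the main one and the registry ones have no severity breakdown. Only the local tolerability summary draws on data recorded with severity.

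**The case against.** **The plan is silent on onset.** A reader might infer that it states that every event since consent is counted. It does not. The sentence quoted from SAP 7.2 is a listing rule, and a listing should show all events. What the text supports is that the table rule carries no treatment-emergent restriction.

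**Treatment-emergent tables by arm already exist in the plan.** This is correct, so a comparison free of pre-dose events will be available. But those tables separate serious from non-serious events and so give no overall treatment-emergent incidence per arm, and their key term is undefined.

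**Severity is not wholly absent.** A reader might infer that it is never summarized. Local tolerability data are summarized by arm, and every event's severity can appear in the listing. What is missing is a general AE or SAE table by severity.

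**The effect is small and its inputs are assumed.** The difference moves by 1.1 to 2.4 points. With about 50 patients per arm, its standard error at 60% vs 45% is √(0.60 × 0.40/50 + 0.45 × 0.55/50) = 9.9 points. A pre-dose rate equal to placebo may be too high: there are no injections in that period and the run-in needs no site visit. The half-rate case above shows the smaller effect. The analysis is descriptive, with no safety test or margin. All of this stands, and it limits the size of the point.

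**Layouts may sit elsewhere.** SAP 1.1 refers to several RAP documents, and only the SAP is available here. Table shells could supply both items, but an onset rule and an endpoint summary belong in the SAP text.

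**Conclusion.** The point holds in a limited form. As written, the main incidence table does not exclude events from the 3 to 7 weeks before first dose. Its likely effect is modest dilution: a risk ratio of 1.33 becomes 1.23 to 1.28 under the assumed rates, and less dilution follows if pre-dose events are rarer than placebo events. The direction requires only that pre-dose events occur about equally in both arms, which randomization gives in expectation; the size depends on rates that the documents do not provide.

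A reader might go further and infer a bias for or against secukinumab. The documents do not support that, because pre-dose events precede any difference in treatment.

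The severity gap is independent of these figures: one named component of the secondary safety endpoint has no general summary by arm. Both are worth correcting because the remedy is specific and the data are already collected.

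**What to change.** In SAP 7.2, with matching wording in protocol 11.4.4 and 11.5.2:

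1. Define treatment-emergent once, as onset or worsening on or after the first dose of study drug.
2. Apply that definition to the main AE and SAE incidence tables and to the registry disclosure tables.
3. List events with onset before first dose separately.
4. Add an AE/SAE table by maximum severity and treatment arm, within body system and preferred term.

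The cost is wording and one extra table. Severity and start dates are already on the CRF, so no new data are needed.

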7.3 Graphical presentation

Boxplots to visualize trends in longitudinal safety data (vitals, ECG, lab parameter) will be created.

8 Appendices

8.1 Appendix 1

Computing EQ-5D-5L crosswalk index values with SAS using the United States (US) value set

The variables for the 5 dimensions of the EQ-5D-5L descriptive system should be named 'mobility', 'selfcare', 'activity', 'pain', and 'anxiety'. If they are given different names the syntax code below will not work properly. The 5 variables should contain the values for the different dimensions in the EQ-5D health profile (i.e. 1, 2, 3, 4 or 5). The variable 'EQindex' contains the values of the EQ-5D-5L crosswalk index values on the basis of the US set of weights.

You can copy and paste the syntax below directly into a SAS syntax window.

```
*****
*SAS syntax code for the computation of index*
*values with the US TTO value set*
*****;

data Euroqol.US_tto;
set Euroqol.EQ5D_states;
EQindex = .;

if (mobility=1 and selfcare=1 and activity=1 and pain=1 and anxiety=1) then EQindex = 1.000;
if (mobility=1 and selfcare=1 and activity=1 and pain=1 and anxiety=2) then EQindex = 0.876;
if (mobility=1 and selfcare=1 and activity=1 and pain=1 and anxiety=3) then EQindex = 0.844;
if (mobility=1 and selfcare=1 and activity=1 and pain=1 and anxiety=4) then EQindex = 0.700;
if (mobility=1 and selfcare=1 and activity=1 and pain=1 and anxiety=5) then EQindex = 0.550;
if (mobility=1 and selfcare=1 and activity=1 and pain=2 and anxiety=1) then EQindex = 0.861;
if (mobility=1 and selfcare=1 and activity=1 and pain=2 and anxiety=2) then EQindex = 0.820;
if (mobility=1 and selfcare=1 and activity=1 and pain=2 and anxiety=3) then EQindex = 0.809;
if (mobility=1 and selfcare=1 and activity=1 and pain=2 and anxiety=4) then EQindex = 0.669;
if (mobility=1 and selfcare=1 and activity=1 and pain=2 and anxiety=5) then EQindex = 0.524;
if (mobility=1 and selfcare=1 and activity=1 and pain=3 and anxiety=1) then EQindex = 0.827;
if (mobility=1 and selfcare=1 and activity=1 and pain=3 and anxiety=2) then EQindex = 0.806;
if (mobility=1 and selfcare=1 and activity=1 and pain=3 and anxiety=3) then EQindex = 0.800;
if (mobility=1 and selfcare=1 and activity=1 and pain=3 and anxiety=4) then EQindex = 0.661;
if (mobility=1 and selfcare=1 and activity=1 and pain=3 and anxiety=5) then EQindex = 0.517;
if (mobility=1 and selfcare=1 and activity=1 and pain=4 and anxiety=1) then EQindex = 0.682;
if (mobility=1 and selfcare=1 and activity=1 and pain=4 and anxiety=2) then EQindex = 0.663;
if (mobility=1 and selfcare=1 and activity=1 and pain=4 and anxiety=3) then EQindex = 0.659;
if (mobility=1 and selfcare=1 and activity=1 and pain=4 and anxiety=4) then EQindex = 0.544;
if (mobility=1 and selfcare=1 and activity=1 and pain=4 and anxiety=5) then EQindex = 0.426;
if (mobility=1 and selfcare=1 and activity=1 and pain=5 and anxiety=1) then EQindex = 0.463;
if (mobility=1 and selfcare=1 and activity=1 and pain=5 and anxiety=2) then EQindex = 0.450;
if (mobility=1 and selfcare=1 and activity=1 and pain=5 and anxiety=3) then EQindex = 0.446;
if (mobility=1 and selfcare=1 and activity=1 and pain=5 and anxiety=4) then EQindex = 0.369;
if (mobility=1 and selfcare=1 and activity=1 and pain=5 and anxiety=5) then EQindex = 0.289;
if (mobility=1 and selfcare=1 and activity=2 and pain=1 and anxiety=1) then EQindex = 0.888;
if (mobility=1 and selfcare=1 and activity=2 and pain=1 and anxiety=2) then EQindex = 0.846;
if (mobility=1 and selfcare=1 and activity=2 and pain=1 and anxiety=3) then EQindex = 0.835;
if (mobility=1 and selfcare=1 and activity=2 and pain=1 and anxiety=4) then EQindex = 0.695;
if (mobility=1 and selfcare=1 and activity=2 and pain=1 and anxiety=5) then EQindex = 0.550;
```

```
if (mobility=5 and selfcare=5 and activity=5 and pain=3 and anxiety=1) then EQindex = 0.145;  
if (mobility=5 and selfcare=5 and activity=5 and pain=3 and anxiety=2) then EQindex = 0.124;  
if (mobility=5 and selfcare=5 and activity=5 and pain=3 and anxiety=3) then EQindex = 0.118;  
if (mobility=5 and selfcare=5 and activity=5 and pain=3 and anxiety=4) then EQindex = 0.075;  
if (mobility=5 and selfcare=5 and activity=5 and pain=3 and anxiety=5) then EQindex = 0.030;  
if (mobility=5 and selfcare=5 and activity=5 and pain=4 and anxiety=1) then EQindex = 0.078;  
if (mobility=5 and selfcare=5 and activity=5 and pain=4 and anxiety=2) then EQindex = 0.060;  
if (mobility=5 and selfcare=5 and activity=5 and pain=4 and anxiety=3) then EQindex = 0.055;  
if (mobility=5 and selfcare=5 and activity=5 and pain=4 and anxiety=4) then EQindex = 0.015;  
if (mobility=5 and selfcare=5 and activity=5 and pain=4 and anxiety=5) then EQindex = -0.026;  
if (mobility=5 and selfcare=5 and activity=5 and pain=5 and anxiety=1) then EQindex = -0.024;  
if (mobility=5 and selfcare=5 and activity=5 and pain=5 and anxiety=2) then EQindex = -0.037;  
if (mobility=5 and selfcare=5 and activity=5 and pain=5 and anxiety=3) then EQindex = -0.040;  
if (mobility=5 and selfcare=5 and activity=5 and pain=5 and anxiety=4) then EQindex = -0.074;  
if (mobility=5 and selfcare=5 and activity=5 and pain=5 and anxiety=5) then EQindex = -0.109;  
  
if (mobility = .) or (selfcare = .) or (activity = .) or (pain = .) or (anxiety = .) then EQindex = . ;  
  
output;  
run;
```
